6.1.4. Handling of Dropouts or Missing Data

6.1.4.1. Imputation of Missing Data

Any subject who prematurely withdraws from the study will have their last available data assigned to an analysis window as described in Section 6.1.5.

For the primary efficacy endpoint of S-IGA score, the primary analysis will impute missing values using a regression-based multiple imputation model. This is a three step process.

1. The first step is to understand the pattern of missingness. In order to perform the multiple imputation, a monotone missing pattern has to be achieved. For example, if there exists values for baseline and Week 8 visits, but missing values for the Week 2 or 4 visits, Markov-Chain Monte-Carlo (MCMC) method will be used to impute the small amount of missing data that may be missing at the intermediate visits that is required to make the missing data pattern monotone before applying the multiple imputation algorithm. This method uses a non-informative Jeffreys prior to derive the posterior mode from the expectation-maximization (EM) algorithm as the starting values for the MCMC method. MCMC method will use seed of 34978264. The S-IGA score will be treated as a continuous variable for this step. To avoid values that could not be observed in practice, imputed values will be constrained to be integers in the range of 0 to 4.
 - a. The table below will determine the number of datasets to be imputed in this step. Determine the proportion of datapoints with non-monotone pattern across all visits and subjects which could be derived as a percentage of number of nonmonotone data points/total number of expected data points.

This can be determined as $\frac{\text{number of non monotone visits}}{\text{total number of visits across all subjects}} * 100$

Non-monotone Missing Data	Number of Imputed Datasets
≤ 2%	1
> 2% to ≤ 5%	3
> 5%	10

2. Once the monotone pattern is achieved, the next step is to implement the imputation algorithm. For this, the Predictive Mean Matching method (PMM) will be used. This method is particularly helpful if the normality assumption is violated. For subjects with complete data up to a particular visit, a PMM model will be fit that includes the outcome at that visit as the dependent variable and as independent variables, S-IGA score outcomes at previous visits, treatment group, and country using a seed of 51192215. This process will be repeated 25 times, resulting in a total of 25 to 250 complete analysis

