datasets, depending on the number of imputed monotone datasets that are required. The seed may be changed after unblinding in case of any issues with the imputation process, and it will be documented in the CSR if any change is required.

3. For each completed dataset, compute the necessary derived variables. The dichotomous success rate (clear or almost clear with at least a 2-point change from baseline) will be derived. The results obtained will be analyzed using the Cochran-Mantel-Haenszel (CMH) analysis for each of the complete analysis data sets stratified by baseline S-IGA score category, baseline B-IGA score category, and country. The results will be combined into one multiple imputation inference (odds ratio, associated CI, and *P* value) using PROC MIANALYZE as illustrated⁴.

This approach to imputation should be superior to other strategies such as carrying forward the last available observation, which may yield unrealistic imputed values. Also, the use of multiple imputation avoids the problem of artificially increasing power through data imputation associated with single-imputation methods because it accounts for the uncertainty associated with the imputation. Other missing data will not be imputed, with the exception of incomplete dates as described in Section 6.1.8. For responder analyses, missing data will be treated as a nonresponse with the exception of S-IGA. Only observed data will be summarized using descriptive statistics.

The SAS pseudo code for the multiple imputation process is listed below:

Step 1:

```
proc mi data=example seed=34978264 nimpute=XX round=1 out=example_1;  
  mcmc impute=monotone;  
  var <baseline score> ..... <visit8 score>;  
run;
```

Step 2:

```
proc mi data=example_1 seed=51192215 nimpute=XX out=example_2;  
  class <treatment> <country>;  
  monotone regpmm(<baseline score> ..... <visit8 score>);  
  var <treatment> <country> <baseline score> ..... <visit8 score>;  
run;
```

XX will be determined based on the proportion of missing data across visits.

Step 3: This step involves running CMH test stratified by baseline S-IGA score category, baseline B-IGA score category, and country on each completed dataset and combining the results using PROC MIANALYZE.

```
proc freq data=example noprint;  
  by <imputationnumber> <visit> ;  
  tables <country> * <BL S-IGA cat> * <BL B-IGA cat> * <treatment> *  
    <outcome> / cmh alpha=0.05;  
  output out=example_stat cmh;  
run;
```

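### The pseudo-code for the primary multiple imputation conflicts with the SAP text: Step 2 has no BY on the Step 1 index, one XX sets both draw counts, and Step 3 names the un-imputed file

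*SAP*

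**What the plan says.** The text of SAP 6.1.4.1 has three steps.

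- **Step 1** fills intermediate gaps by MCMC until the missing pattern is monotone. On the number of copies it says: "The table below will determine the number of datasets to be imputed in this step". The table gives 1 copy if at most 2% of data points are non-monotone, 3 if more than 2% and up to 5%, and 10 above 5%. Imputed values must be integers from 0 to 4.
- **Step 2** applies predictive mean matching, with "S-IGA score outcomes at previous visits, treatment group, and country using a seed of 51192215". On the number of draws: "This process will be repeated 25 times, resulting in a total of 25 to 250 complete analysis" files, the total being set by how many monotone copies Step 1 needs.
- **Step 3** derives success and runs the CMH test on each completed data set, then pools with PROC MIANALYZE. SAP 8.1.1 repeats that each data set is tested separately.

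The pseudo-code in the same section reads differently.

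- Step 1 is "proc mi data=example seed=34978264 nimpute=XX round=1 out=example_1" with "mcmc impute=monotone". It rounds, but codes no 0 and 4 limits.
- Step 2 is "proc mi data=example_1 seed=51192215 nimpute=XX out=example_2", followed by CLASS, MONOTONE and VAR statements only.
- One rule, based on the proportion of missing data, is given for XX. The figure 25 appears nowhere in the code.
- Step 3 runs PROC FREQ on `example`, the file that Step 1 takes as its un-imputed input, BY one imputation number and visit.

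SAP 6.1.4.2 repeats the Step 2 block for the tipping-point analysis, again without BY and with XX.

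**The concern.** When Step 1 makes 3 or 10 copies, `example_1` holds every subject 3 or 10 times. A second PROC MI call without BY fits one model to all those rows, and each of its output data sets again holds every subject 3 or 10 times. A CMH test by the new imputation number then counts the copies as independent subjects. The odds ratio barely moves, but its standard error is far too small.

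This is the only code given for the primary test, and SAP 6.1.3 makes every secondary test depend on that result. The authors write BY where they want it (in PROC FREQ, and spelled out again in 6.1.4.2), so its absence from Step 2 is not obviously shorthand. A programmer has to settle the BY statement, the value of XX and the Step 3 input alone. Those choices belong in the plan before unblinding.

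**Working it through.** **Inputs.** Copies from Step 1: M = 1, 3 or 10 (SAP 6.1.4.1 table). Draws per copy: N = 25 (6.1.4.1 text). Two-sided alpha 0.05 (8.1.1). About 200 and 100 subjects, 300 in total (3.2).

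**1. The plan's own count.** N × M = 25 × 1, 3, 10 = 25, 75, 250. This reproduces the stated range of 25 to 250. The range is possible only if Step 2 runs within each Step 1 copy.

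**2. The count the code gives.**

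| | M = 1 | M = 3 | M = 10 |
|---|---|---|---|
| Text: 25 draws within each copy | 25 sets of 300 | 75 sets of 300 | 250 sets of 300 |
| Code as written: same XX, no BY | 1 set of 300 | 3 sets of 900 | 10 sets of 3,000 |
| BY added, same XX kept | 1 × 1 = 1 | 3 × 3 = 9 | 10 × 10 = 100 |

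Neither code row agrees with the text for any M.

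**3. Effect of stacking.** Repeating every cell of each stratum M times leaves the Mantel-Haenszel odds ratio unchanged and divides the variance of its logarithm by M. The standard error is multiplied by 1/√M, and the actual two-sided alpha is 2 × [1 − Φ(1.96/√M)].

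- M = 3: factor 0.577; 1.96/1.732 = 1.132; alpha = 25.8%.
- M = 10: factor 0.316; 1.96/3.162 = 0.620; alpha = 53.5%.
- M = 1: factor 1; alpha = 5%.

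**4. Simulation under no treatment effect.** It used 200 and 100 subjects, predictive mean matching, N = 25 and the Mantel-Haenszel log odds ratio. Assumptions not in the documents: 10% dropout, 3.5% (M = 3) or 6% (M = 10) non-monotone data, two strata, country left out, and intermittent gaps only in subjects with an observed Week 8 score.

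| | M = 3 (1,500 runs) | M = 10 (250 runs) |
|---|---|---|
| Type I error, copies stacked | 26.7% | 56.4% |
| Type I error, BY with 25 draws | 4.4% | 4.4% |
| Mean standard error, stacked | 0.166 | 0.091 |
| Mean standard error, BY with 25 draws | 0.288 | 0.288 |

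**5. The case M = 1.** Nothing is stacked. But if XX = 1 also applies to Step 2, there is one draw, no between-imputation variance, and nothing for PROC MIANALYZE to combine. SAP 6.1.4.1 itself gives avoidance of the false precision of single imputation as a reason for its method. The size depends on how many Week 8 scores are missing and was not computed.

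**6. Pooling once BY is added.** The 75 or 250 data sets are then nested, and no nested rule is named. The nested variance is T = Ū + (1 − 1/N)W + (1 + 1/M)B, where Ū is the mean complete-data variance, W the within-copy variance and B the between-copy variance. In the simulation the single-level and nested standard errors were 0.28791 and 0.28795 (M = 3), and 0.28783 and 0.28785 (M = 10): a difference under 0.02%. If as much as 5 to 10% of total variance came from Step 1, alpha would be 5.4 to 5.8% (M = 3) or 5.1 to 5.2% (M = 10).

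**The case against.** The strongest reply is that the block is labelled pseudo-code, with placeholders and an undefined XX, and that the text is unambiguous. This largely stands. A reader might infer that the plan itself would test stacked copies as one data set. The documents do not support that: 6.1.4.1 and 8.1.1 call for 25 to 250 data sets tested separately.

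Nor does the code run word for word produce the 26% and 54% figures. Step 3 as written reads `example`, so it would not test imputed data at all. The figures assume that this line is corrected and Step 2 is not. One could take `example` as a loose placeholder, but Step 1 uses the same name for the un-imputed source.

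Stacking also needs more than 2% non-monotone data. SAP 6.1.4.1 expects little, and the COVID-19 cases that define the mITT population (Week 8 missed, or discontinuation before Week 8) do not by themselves create intermediate gaps. On the other side, SAP 6.2 allows for missed visits in general and rules out remote S-IGA. If the denominator is 300 subjects × 3 to 5 visits (an assumption, since the visits are not listed), 2% is only 18 to 30 missed intermediate assessments.

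Two further readings are tempting. One is that pooling nested imputations with single-level rules materially understates the variance. Stacking and nesting exclude each other: without BY nothing is nested, and with BY nothing is stacked. The nested effect is also negligible here, because Step 1 fills only visits that precede an observed score, so an observed Week 8 outcome is never replaced. The other is that omitting treatment from Step 1 and baseline B-IGA category from Step 2 biases the estimate. With 10% Week 8 and 5% intermittent missing data assumed, simulation put the change in the Week 8 difference under 0.1 percentage points.

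**Conclusion.** The concern holds as a conflict between code and text. The pseudo-code for the primary analysis, and its copy for the tipping-point analysis, cannot yield the data sets that the SAP text requires.

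The consequence is conditional. With more than 2% non-monotone data, Step 2 run without BY and its output tested, two-sided type I error is about 26% with 3 copies or 54% with 10, against 5%. At 2% or less, the shared XX would reduce Step 2 to a single imputation. Followed as the text describes, the method is sound (4.4% in simulation under the assumptions above). Neither the pooling rule nor the missing model terms carry weight. The correction should still be made before unblinding, because the cost is small and the code is not safe to run as it stands.

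**What to change.** Align the code with the text.

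- **Step 1:** keep the 1, 3 or 10 table, code the 0 and 4 limits alongside the rounding, and store the imputation index under its own name.
- **Step 2:** run BY that index with nimpute=25. Reserve XX for Step 1.
- **Step 3:** read `example_2`, after success has been derived from it, BY both indices and visit. Form one running index for PROC MIANALYZE and state the pooling rule.
- **Section 6.1.4.2:** make the same BY and nimpute corrections, and carry both indices with the shift parameter.

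An acceptable equivalent is 25 Step 1 draws with one Step 2 draw each, run BY the Step 1 index. This gives 25 data sets and removes the nested-pooling question, but it replaces the 1, 3 or 10 table. Adding baseline B-IGA category to the imputation model is an optional tidy-up with no material effect.

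The cost is a few lines of SAP text and code. No data collection, sample size or test changes.

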For this study, the primary estimand is the odds of achieving S-IGA success at 8 weeks; that is, the ratio of the odds of achieving S-IGA success at 8 weeks roflumilast foam 0.3% relative to the odds of success at 8 weeks of using a matching vehicle cream. In the course of the 8-week randomized treatment period, subjects may be exposed to possible known or unknown intercurrent events that could possibly impact the estimand, such as treatment discontinuation due to a specific adverse effect or perhaps a lack of effect. The “Treatment Policy Strategy” has been adopted for handling all known or unknown intercurrent events in this study. To this end, the ITT principle will serve as the analytical basis for interpreting the estimand. In other words, the odds ratio of achieving S-IGA success for roflumilast foam 0.3% relative to vehicle at 8 weeks will be evaluated regardless of the occurrence of any such intercurrent event. This estimand shall be estimated using the CMH approach. This approach produces an estimate that is the combined odds ratio resulting from adjusting for the possible effects of 3 classification factors: country, baseline S-IGA category (2 vs. ≥ 3) and baseline B-IGA category (2 vs. ≥ 3).

Categorical Data Analysis

The primary efficacy endpoint is success in S-IGA of disease severity, defined as an S-IGA of “Clear” or “Almost Clear” plus a 2-grade improvement from baseline at Week 8.

The primary endpoint will be analyzed using a CMH test stratified by country, baseline S-IGA category, and baseline B-IGA category. Statistical significance will be concluded at the 5% significance level (2-sided) or less, as discussed in Section 6.1.3. Odds ratios and 95% CIs for the odds ratios will be provided. Additionally, the 95% Wilson CIs for proportion of successes in each treatment group will be presented.

For the primary analysis, missing S-IGA scores will be imputed using multiple imputation as described in Section 6.1.4.1. These imputations will result in a minimum of 25 to a maximum of 250 complete analysis datasets, depending on the number of imputed monotone datasets required. The CMH analyses will be performed separately for each of the complete analysis data sets, and the results will be combined into one multiple imputation inference (estimated treatment effect and associated CI and *P* value). As a sensitivity analysis, the above described CMH test will be performed on the nonimputed data.

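### The pseudo code for the primary multiple imputation contradicts the SAP text and cannot produce the 25 to 250 completed datasets that the text requires; programmed in place of the text, it could undo type I error control.

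*SAP*

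**What the plan says.** **Text.** SAP 6.1.4.1 describes a nested imputation. Step 1 (MCMC) fills intermediate gaps to make the missing pattern monotone. On the number of copies, "The table below will determine the number of datasets to be imputed in this step": 1 copy if non-monotone data are at most 2%, 3 if above 2% and up to 5%, and 10 if above 5%. For Step 2 (predictive mean matching), "This process will be repeated 25 times, resulting in a total of 25 to 250 complete analysis" datasets. Section 8.1.1 repeats the count ("These imputations will result in a minimum of 25 to a maximum of 250 complete analysis datasets"), has the CMH run separately on each set, and pools the results. On the pooled result, "Statistical significance will be concluded at the 5% significance level (2-sided) or less".

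**Listing.** The pseudo code in the same section reads differently:

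- Step 1 writes its copies to one file, `example_1`.
- Step 2 is "proc mi data=example_1 seed=51192215 nimpute=XX out=example_2", with no BY statement. The tipping-point Step 2 code in 6.1.4.2 has the same line and the same omission.
- The placeholder used in both steps has one definition: "XX will be determined based on the proportion of missing data across visits".
- Step 3 runs PROC FREQ on `example`, the Step 1 input, with "by <imputationnumber> <visit>". The imputation-number placeholder is not defined.

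**The concern.** The text and the listing specify different analyses for the primary endpoint. Without a BY statement, PROC MI treats a stacked file as one sample. (This is standard software behaviour, not something the SAP states.) With 3 or 10 Step 1 copies, one imputation model would then be fitted to 3N or 10N rows, and each Step 2 output set would hold every subject 3 or 10 times. A CMH test on such a set uses a reference distribution that assumes N independent subjects.

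The P value at stake is the primary one, and under SAP 6.1.3 it opens the gate to every secondary test. Separately, if XX carries its Step 1 value into Step 2, the lowest tier gets one imputation. That is the single-imputation weakness that 6.1.4.1 gives as a reason for choosing multiple imputation.

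**Working it through.** **1. The SAP's own count.** 25 × {1, 3, 10} = 25, 75, 250. This reproduces the stated range of 25 to 250, but only if Step 2 runs within each Step 1 copy.

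**2. What the listing gives.** Let k be the number of Step 1 copies, and let Step 3 be pointed at `example_2`:

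| Reading of the listing | k=1 | k=3 | k=10 |
|---|---|---|---|
| Text (required) | 25 | 75 | 250 |
| XX in Step 2, grouped by Step 2 index | 1 | 3 | 10 |
| XX in Step 2, grouped by both indices (k×k) | 1 | 9 | 100 |
| 25 in Step 2, grouped by Step 2 index | 25 | 25 | 25 |
| 25 in Step 2, grouped by both indices | 25 | 75 | 250 |

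Only the last row matches for every k. It needs a value and an index that the listing does not supply, and for k above 1 the imputation model is still fitted to duplicated subjects. Taken literally, Step 3 reads `example`, which holds no imputations.

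**3. Size of the test if copies are stacked.** Repeating every subject k times multiplies the CMH chi-square by about k. At a nominal two-sided 5% the critical value is 3.8415, so the size is P(χ²₁ > 3.8415/k):

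- k=1: P(χ²₁ > 3.8415) = 5.0%
- k=3: P(χ²₁ > 1.2805) = 25.8%
- k=10: P(χ²₁ > 0.3841) = 53.5%

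The odds-ratio interval on the log scale is too narrow by a factor of about √3 = 1.7 or √10 = 3.2.

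**4. Simulation under no treatment effect.** Both simulations used 300 subjects at 2:1. Missing-data rates and strata are assumptions, because the documents give none.

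| Setting | k | Stacked | Nested as in the text |
|---|---|---|---|
| A: 12% dropout, 6 strata | 1 | 4.5% | 5.0% |
| A | 3 | 23.8% | 5.0% |
| A | 10 | 47.7% | 5.3% |
| B: 5% dropout, 8 strata | 1 | 5.0–6.3% | 6.0% |
| B, 5% dropout | 3 | 25.0% | 4.0–4.3% |
| B, 5% dropout | 10 | 53.2–54.0% | 3.6–4.0% |
| B, 15% dropout | 1 | 4.0–4.3% | 3.8–4.0% |
| B, 15% dropout | 3 | 22.8–23.8% | 3.5–4.0% |

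Ranges in B cover two ways of pooling: the Wilson-Hilferty transform and the log odds ratio. B used 25 Step 2 imputations in the stacked runs, so it isolates the missing BY and does not test XX=1. Its nested k=10 run used 5 per copy, and its k=10 run at 15% dropout was not completed. B ran 400 trials per setting (250 for k=10), so Monte Carlo standard errors are about 2 points near 25%, 3 points near 54% and 1 point near 4%.

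**5. When k exceeds 1.** With 300 subjects and 3 or 4 S-IGA time points (Weeks 2, 4 and 8, with or without baseline) there are 900 or 1,200 values. Two per cent is 18 or 24 gaps, and five per cent is 45 or 60. More than the first number gives k=3; more than the second gives k=10.

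**6. XX=1 in Step 2.** With one imputation, no between-imputation variance can be estimated. As an illustration, let f be the fraction of missing information (assumed). The true variance relative to the one used is 1 + 2f/(1−f), and the size is 2[1 − Φ(1.96/√that)]:

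- f=5%: 1.105, size 6.2%
- f=10%: 1.222, size 7.6%
- f=20%: 1.500, size 11.0%

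**The case against.** The strongest reply is that the text governs. It is explicit, appears in two sections and gives the right method. The listing is labelled pseudo code and leaves out other things the text requires, such as the 0 to 4 limits in Step 1, the derivation of success and the PROC MIANALYZE call. A missing BY may be no more than that style. This stands as evidence of intent, and a careful programmer could recover the nested method. It does not make the listing right: a BY is written in Step 3 and in the tipping-point PROC FREQ, and the only definition of XX conflicts with 25.

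A reader might infer that, run as written, the primary test rejects a true null 24–54% of the time. The documents do not support that, for four reasons:

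- Literal Step 3 reads the unimputed file, so literal execution stacks nothing.
- The undefined imputation number could index both steps, which would separate the copies in the CMH. It would not repair a Step 2 model fitted to duplicated subjects.
- Stacking needs more than 2% non-monotone data, while the SAP expects a "small amount of missing data that may be missing at the intermediate visits". A missed Week 8 visit or dropout is monotone, and the contiguous windows in 6.1.5 let unscheduled assessments fill gaps. Against this, 6.2 expects visits missed through COVID-19 and bars remote S-IGA, so missed Week 2 or Week 4 assessments followed by an attended Week 8 are plausible. The documents give no rate.
- Stacking should be noticed. The imputed-data table shells show counts by visit against the ITT total, and CMH and GEE analyses on nonimputed data are also planned.

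These points lower the probability of harm. They do not remove the contradiction. Section 6.1.4.1 also lets the seed be changed after unblinding if the imputation meets problems, which is a reason to settle the code beforehand.

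**Conclusion.** The specification of the primary analysis is internally inconsistent. As listed, the code cannot deliver the 25, 75 or 250 separately imputed datasets that the text requires, and 6.1.4.2 carries the Step 2 error into the tipping-point analysis. The method described in the text is sound; nested as described, it held its size at about 4–6% in simulation.

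The damage is conditional. It requires more than 2% non-monotone missing data, Step 2 run as listed, and Step 3 applied to `example_2` grouped only by the Step 2 index. Under those conditions the size is about 26% for 3 copies and 54% for 10 analytically, and about 24% and 48–54% in simulation. At 2% or less nothing is stacked, and the remaining risk is a single Step 2 imputation with no between-imputation variance; how much that inflates the size depends on a missing-information fraction that the documents do not give. The conclusion also rests on PROC MI treating an undivided file as one sample.

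**What to change.** Amend the listings in SAP 6.1.4.1 and 6.1.4.2 before unblinding:

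1. Rename the Step 1 imputation index, sort by it, and add it as a BY variable in the Step 2 PROC MI.
2. Set `nimpute=25` in Step 2 and keep XX (1, 3 or 10) for Step 1 only.
3. Have Step 3 read `example_2`. Define one combined index over both steps (1 to 25, 75 or 250) and use it in the primary and tipping-point BY statements.
4. Add a program check that each BY group (combined index by visit) holds exactly the number of ITT subjects, or mITT subjects in the repeat analysis.

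The cost is a few lines of pseudo code and one check. It brings the code into line with the planned method and needs no new data.
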